- a single dose of the trivalent conjugate vaccine, followed by a dose of placebo 28 days later (n=25);
- two doses of trivalent conjugate vaccine, separated by 28 days (n=25);
- or two doses of placebo, separated by 28 days (n=10).

Special Notation: Due to the limited shelf-life of the vaccine, which is being determined by an ongoing stability testing plan, the availability of this pilot production lot of vaccine may be limited in time. Furthermore, since March 2020 the global pandemic due to SARS-CoV-2 virus (causing COVID-19 infections) has significantly disrupted the ability to conduct this study. Therefore, the Step 3 (Cohort C) has been significantly revised such that both a single and two-dose regimens of the 25 μ g dosage of vaccine will be evaluated, albeit with a very small sample size. This was originally intended to be evaluated with a large sample size in Part 2 (Cohort D), but due to the extraordinary present circumstances, the revised design of the study is intended to provide similar information which is crucial for the vaccine development plan. Furthermore, in order to provide some bridging immunogenicity data, a small number of participants in Cohort C will be randomized to receive either a single or two-dose regimen of

the 12.5 µg dosage of the vaccine. It is possible that Part 2 (Cohort D) will not be conducted, due to lack of vaccine.

Furthermore, because of the COVID-19 situation, for Cohort A the follow-up visits at 6 months post-vaccination were conducted by phone call contact and thus the collection of specimens was unable to be conducted. For Cohort B, the follow-up visits at 2 months and 6 months post-vaccination were conducted by phone call contact and thus the collection of specimens was unable to be conducted. Therefore for Cohort A and B participants, a single clinic visit for the collection of blood and oral fluid will be requested to measure the long-term immune responses (>6 months post-vaccination).

Pharmaron CPC, Inc. (Baltimore, MD) is being added as a site for the enrollment of Cohort C.

KEY PERSONNEL

Principal Investigator:

[name], MS, FACP, FIDSA
Professor of Medicine
Chief, Adult Clinical Studies section
Center for Vaccine Development & Global Health
University of Maryland School of Medicine
Direct Office [contact]
Mobile [contact]
Email: [contact]

Clinical Co-Principal Investigator:

[name], MB, ChB, FACP
Pharmaron CPC Inc.
[name]
Baltimore MD 21201
Office: [contact]

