2.3 Primary Objectives and Outcome Measures

The primary objectives and outcome measure of this study are the following:

1. Safety and Reactogenicity: To assess the frequency and severity of solicited local (i.e., injective site) and systemic (such as fever) AEs during the first 7 days following each dose of vaccine.
2. Safety: To assess the frequency and severity of unsolicited AEs within 28 days of each dose of vaccine and the occurrence of any SAEs through 6 months after the last dose of vaccine
3. Immunogenicity: To measure the proportion of subjects that achieve a four-fold increase in titer, as compared to baseline, of specific serum IgG anti-COPS (S. Enteritidis or S. Typhimurium), anti-Vi (S. Typhi) polysaccharide, and anti-FliC (S. Enteritidis or S. Typhimurium) antibody at days 29 and 57, as measured by ELISA.

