2.4 Secondary Objectives and Outcome Measures

The secondary objectives and outcome measures of this study are the following:

1. Safety: To assess the frequency and severity of abnormalities in clinical safety laboratory parameters at 7 days following the first dose of vaccine.
2. Immunogenicity: To measure the proportion of subjects that achieve a four-fold increase in titer, as compared to baseline, of specific serum IgG anti-COPS (S. Enteritidis or S. Typhimurium), anti-Vi (S. Typhi) polysaccharide, and anti-FliCn (S. Enteritidis or S. Typhimurium) antibody at day 180/210, as measured by ELISA.
3. Immunogenicity: To calculate the GMT of serum IgG anti-COPS (S. Enteritidis or S. Typhimurium), anti-Vi polysaccharide, and anti-FliC (S. Enteritidis or S. Typhimurium) antibodies at days 1, 29, 57, and 180/210, as measured by ELISA.

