10 STATISTICAL CONSIDERATIONS

10.1 Study Hypothesis and Sample Size Considerations

The overarching hypothesis of this phase 1 study is that the trivalent *S. Enteritidis/S. Typhimurium/S. Typhi* Vi conjugate vaccine will be well-tolerated at all three dosage levels tested and that the highest dosage level will elicit the strongest serum anti-COPS, anti-FliC and anti-Vi antibody responses in humans. The primary hypothesis of safety will be fulfilled if no participants develop a vaccine related SAE and each vaccine is well-tolerated. The secondary hypothesis of immunogenicity will be fulfilled if each vaccine elicits an immune response by ELISA.

The trial sample size is intended to minimize the number of subjects exposed to each vaccine until sufficient safety data have accumulated to proceed to larger trials. The phase 1 trial sample size was not derived to achieve a pre-specified statistical power. Instead, the sample size was selected to descriptively evaluate the safety and immunogenicity of these vaccines in a first-in-man trial. As a result, there will be sufficient power to detect only very large differences in immunological responses among groups, and confidence limits will be fairly wide.

The endpoint measures for the primary, secondary and exploratory objectives are listed in Sections 6.1, 6.2 and 6.3.

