10.2 General Statistical Principles

Descriptive Statistics. To summarize safety, the number and percentage of participants in each cohort that experiences each AE, categorized by body system and preferred term, will be tabulated with by vaccine received along with a corresponding two-sided exact 95% confidence interval (95%CI). For seroresponse rate endpoints, two-sided 95%CI for each proportion will be calculated. When determining GMT antibody titer, the log values will be used to construct the 95%CI using the t-distribution for the mean difference between three pair-wise vaccine groups. The mean difference and the corresponding CI limits will then be exponentiated to obtain the GMT ratio and corresponding CI. If the values deviate from a log normal distribution, then a non-parametric method may be used for the analysis of GMT.

Continuous Measures of Immune Response. Continuous variables of interest that are not normally distributed will be transformed if needed. To compare each vaccine dose group with the placebo group, t test or Mann-Whitney U test will be used for continuous variables as appropriate

Multiple Comparisons. No formal statistical adjustment for multiple comparisons is planned. The investigators recognize that the study involves multiple comparisons (among vaccine doses, between vaccines, etc.) of safety and immunogenicity parameters, and that statistically significant results could be obtained in some cases when there is no difference between the groups being compared. However, such instances (type I errors) should be infrequent; e.g., if we use $p < 0.05$ as the criterion for statistical significance, only 5% of all comparisons that are actually equivalent will be significant. Moreover, it is difficult to know exactly which comparisons should be included in an adjustment. (We would not want to include safety assessments, because the error of assessing a safe vaccine as unsafe is preferable to thinking that a truly unsafe vaccine is safe.) The main purpose of this trial is to provide data for making decisions about further study of this vaccine, and statistical significance per se is not the only criterion for decision-making in this process. Nevertheless, the investigators will keep the issue of multiple comparisons in mind when interpreting the data and making decisions, even though no formal adjustment is made.

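### Do the uncollected Cohort A and B specimens make the Day 180/210 comparison with placebo unable to reach significance?

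*Combined protocol and SAP*

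**What the plan says.** The Special Notation in the Protocol Synopsis states that "For Cohort B, the follow-up visits at 2 months and 6 months post-vaccination were conducted by phone call contact", that Cohort A's 6-month visit was handled the same way, and that specimens could not be collected. It then adds, for both cohorts, that "a single clinic visit for the collection of blood and oral fluid will be requested to measure the long-term immune responses", more than 6 months after vaccination. It also warns: "It is possible that Part 2 (Cohort D) will not be conducted, due to lack of vaccine".

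The objectives are unchanged. Section 2.3 (primary) covers four-fold rises in "antibody at days 29 and 57, as measured by ELISA". Section 2.4 (secondary) adds the four-fold-rise proportion at Day 180/210 and the GMT of "antibodies at days 1, 29, 57, and 180/210, as measured by ELISA".

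Section 10.2 gives the test: "To compare each vaccine dose group with the placebo group, t test or Mann-Whitney U test will be used for continuous variables as appropriate". Confidence intervals for GMT ratios are built on log values "using the t-distribution for the mean difference between three pair-wise vaccine groups". A non-parametric method is optional if the values are not log normal. Section 10.1 says the sample size was not derived from power and that "there will be sufficient power to detect only very large differences in immunological responses among groups".

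**The concern.** The specimen losses are disclosed, but section 10.2 was not rewritten around them. Each Part 1 cohort has only two placebo participants, so losing Cohorts A and B at six months leaves two placebo values at the scheduled final visit. With so few, an exact rank test has a smallest possible p-value that no titre difference can beat. If that value is above 0.05 in every Cohort C vaccine arm, the Day 180/210 table could show no significant result even when every vaccinee's titre exceeds both placebo titres. A reader might take this for waned immunity. Cohort D may not be run, so Cohort C might supply the only scheduled late data. A related worry is that 6.25 µg was given only in Cohort A, so GMT ratios involving that dosage would have no in-window data at the last visit.

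**Working it through.** **Inputs.** Arm sizes are from section 2 and the Schematic of Study Cohorts in section 2.2; losses are from the Special Notation. The plan's totals reproduce: 8+2+10+2+6+6+4+4+2 = 44 for Part 1, and 44+25+25+10 = 104 overall.

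**Placebo specimens at scheduled visits, pooled over Part 1.** Day 29: 2+2+2 = 6. Day 57 (A and C): 2+2 = 4. Day 180/210 (C only): 2.

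**Smallest exact two-sided Mann-Whitney p.** With n vaccinees all above m placebo values and no ties, p = 2/C(n+m, m).

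| Comparison at Day 180/210 | n v m | Smallest p |
|---|---|---|
| Single 25 µg arm | 6 v 2 | 2/28 = 0.071 |
| Single 12.5 µg arm | 4 v 2 | 2/15 = 0.133 |
| 25 µg, one- and two-dose arms together | 12 v 2 | 2/91 = 0.022 |
| 12.5 µg, one- and two-dose arms together | 8 v 2 | 2/45 = 0.044 |
| Single arms, one A/B placebo returnee pooled | 6 v 3; 4 v 3 | 2/84 = 0.024; 2/35 = 0.057 |
| Single arms, two A/B placebo returnees pooled | 6 v 4; 4 v 4 | 2/210 = 0.0095; 2/70 = 0.029 |
| Single arms, Cohort D placebo pooled (2+10) | 6 v 12; 4 v 12 | 2/18564 = 0.0001; 2/1820 = 0.0011 |

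The first two rows are the concern, and they are correct. Each later row changes one open choice. All but the 4 v 3 case fall below 0.05, though with two placebo values only complete separation gets there.

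**The t test.** The difference needed for p<0.05, in SD of log titre, is t(0.975, n+m−2) × √(1/n+1/m). For 6 v 2 this is 2.00 SD, and for 4 v 2 it is 2.40 SD. For an assumed log10 SD of 0.3 to 0.6, these are about 4- to 16-fold and 5- to 28-fold. Power at true differences of 2, 3 and 4 SD is 54%, 86% and 98% for 6 v 2, and 42%, 74% and 92% for 4 v 2 (noncentral t, equal variances). That agrees with section 10.1's statement about very large differences.

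**Whether the lost specimens are the cause.** Section 10.2 does not say whether placebo is pooled across cohorts. If it is taken within cohort, Cohort C has two placebo participants at every visit, and the 0.071 and 0.133 limits apply at Days 29 and 57 too. The limit then comes from the size of Cohort C, which the Special Notation already calls very small.

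**GMT ratios.** If the three pairs are the three dosages (an assumption), two of three lack in-window data at Day 180/210, or 2×5 = 10 of 15 over five ELISA antigens. That reading forms groups by dosage, and the same grouping brings the rank test to 0.022 and 0.044. The two criticisms therefore rest on different readings of one section.

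**The alternative.** One could drop the placebo test at this visit and report within-participant fold rises. The 95% half-widths would be t(5)/√6 = 1.05 and t(3)/√4 = 1.59 SD of the log change, against 2.00 and 2.40 SD of log titre. The units differ. With equal variances and no correlation between the two visits, the SD of the change is √2 times the SD of titre, so 1.05 becomes 1.48 and 1.59 becomes 2.25. The gain is then modest for six-person arms and slight for four-person arms.

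**The case for a change.** The strongest reply is that nobody can judge from two placebo values whether a t test or a rank test is appropriate, yet that choice decides whether significance is attainable in a single arm. The schematic lists one- and two-dose arms separately, so arm-by-arm comparison is a natural reading. The late visit is only requested, has no upper time limit, and is not mapped to the Day 180 ±14 window. For an exact rank test by arm on scheduled samples, power is zero even for very large differences.

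What stands is that section 10.2 leaves open the placebo pooling, the forming of dose groups, the choice of test and the labelling of late samples. Analysts ordinarily settle and record such points before unblinding, and the text points towards an answer. For titres it works on the log scale with the t-distribution and treats the non-parametric method as a fallback. It admits to the immunogenicity analysis anyone with one pre- and one post-vaccination specimen, without a visit window. A pair with no data is simply not reported.

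The misreading risk is small. The planned Day 180/210 results include GMTs and four-fold-rise proportions from each participant's own baseline, with the proportions carrying 95% intervals, so persistence would not be judged from a bare p-value. Section 10.2 itself says significance is not the only criterion.

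**Conclusion.** The missed collections, the two remaining in-window placebo participants and the 0.071 and 0.133 limits are all confirmed. They make significance unattainable only if the exact two-sided Mann-Whitney test is chosen over the t test, Cohort C arms are kept separate, too few Cohort A or B placebo returnees are pooled (none for the six-person arms, at most one for the four-person arms), and Cohort D placebo is absent or unpooled. The plan commits to none of these choices.

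Replacing the placebo comparison with a within-arm fold rise would trade a randomised contrast, which the t test can still inform, for one that does not correct for assay drift or natural exposure and is largely covered by planned summaries. Day 29, the interim analysis on 28-day data and every stated dose decision are untouched. The plan claims no power figure that this contradicts. This is a gap that analysts can fill sensibly in a secondary, descriptive comparison, and no change to the plan is needed.

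The figures assume a two-sided 0.05 level (section 10.2 gives 0.05 only as an example), no ties, no further dropout in Cohort C and, for the t test, normal log titres with equal variances.

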1 BACKGROUND

1.1 Epidemiology and Burden of Disease

Salmonella enterica serovars Typhi and Paratyphi A and B and certain non-typhoidal *Salmonella enterica* (NTS) serovars are important causes of invasive *Salmonella* disease worldwide. “Typhoid Fever” is caused by *Salmonella enterica* serovar Typhi (S. Typhi), while “Paratyphoid Fever” is caused by *Salmonella enterica* serovar Paratyphi A (S. Paratyphi A) or *Salmonella enterica* serovar Paratyphi B (S. Paratyphi B). Both Typhoid Fever and Paratyphoid Fever manifest as persistent fevers, abdominal discomfort, headache and malaise. Without prompt and effective antibiotic treatment, these infections may lead to intestinal hemorrhage, intestinal perforation and peritonitis, myocarditis, hepatitis, neurological consequences and death. In the pre-antibiotic era the case fatality rate of typhoid fever was circa 15%.

In industrialized countries in North America, Europe and in Australia and New Zealand, various NTS serovars are common causes of gastroenteritis, as the result of sporadic food-borne transmission or associated with outbreaks. In older children and adults, these NTS infections typically result in uncomplicated diarrheal illness that does not require antibiotic treatment and invasive infections due to NTS serovars in healthy adults are rare. However, among certain sub-populations (such as infants < 3 months of age, the elderly, and immunocompromised hosts) in industrialized countries, invasive NTS (iNTS) infections such as bacteremia, septicemia, and meningitis can be observed and are associated with notable case fatality.^{2,3} The most common *Salmonella* serovars associated with invasive disease in the U.S. include: S. Typhimurium, S. Enteritidis, S. Heidelberg, S. Dublin, and S. Schwarzengrund.⁴

Whereas invasive disease due to NTS (bacteremia, septicemia, meningitis, etc.) is relatively rare in the USA and industrialized countries, a recognized burden of iNTS disease exists in sub-Saharan Africa, where it was recently estimated that ~2 million cases (~227 cases/100,000 infants and young children) occur annually.⁵ The case fatality ratio of iNTS disease in Africa is ~20%, resulting in an estimated ~681,000 deaths each year.⁵ In sub-Saharan Africa four serovars, S. Typhimurium, S. Enteritidis, I:4,[5],12:i-, and S. Dublin, account for > 85-95% of all iNTS cases.^{6,7} Notably, the strains of S. Typhimurium, I:4,[5],12:i- and S. Enteritidis associated with invasive NTS disease in sub-Saharan Africa are genetically distinct from strains of those serovars circulating in the USA and Europe.^{8,9} For example, S. Typhimurium and I:4,[5],12:i- strains in the USA and Europe are overwhelmingly of multi-locus sequence type ST19, whereas the African strains are ST313, an unusual MLST type. Similarly, the S. Enteritidis strains in Africa are genetically distinct. Notably, most cases of iNTS in infants and toddlers in sub-Saharan Africa do not present with or have a history of gastroenteritis. The vast majority of the iNTS isolates from sub-Saharan Africa encode resistance to multiple clinically-relevant antibiotics.^{8,10}

1.2 Vaccine Development

To address this important public health problem, iNTS vaccines are being developed.^{11,12} The polysaccharides of encapsulated bacteria (e.g., *Haemophilus influenzae* type b, *Streptococcus pneumoniae*, *Neisseria meningitidis*) linked to carrier proteins have resulted in safe, immunogenic (in young children) and highly effective parenteral polysaccharide conjugate

vaccines. One typhoid polysaccharide conjugate vaccine, Typbar-TCV®, manufactured by Bharat Biotech, Hyderabad, India, that was first licensed in India, was pre-qualified in 2017 by the World Health Organization (WHO) for procurement by United Nations Agencies and its use in infants as young as six months of age has been recommended by WHO's Scientific Group of Experts (SAGE).^{13,14} In contrast, currently there are no licensed NTS vaccines.

CVD investigators have been developing candidate polysaccharide protein conjugate vaccines for the prevention of iNTS disease. The vaccine development strategy involves targeting two surface virulence antigens of the key NTS *Salmonella* serovars including the core polysaccharide and O-polysaccharide (COPS) plus FliC protein, the unpolymerized flagellin subunits of flagella motility organelles.^{12,15-19}

The outer membrane lipopolysaccharides of *Salmonella* can be divided into 3 distinct regions: an endotoxin lipid A moiety; a highly conserved, core oligosaccharide region; and a serogroup-specific, repeating oligosaccharide polymer (O-polysaccharide [OPS]). The majority of human invasive isolates fall antigenically within *Salmonella* group A (includes *S. Paratyphi A*), Group B (includes *S. Paratyphi B*, *S. Typhimurium* and I:4,[5],12:i-), Group C (includes *S. Paratyphi C*, *S. Choleraesuis* and *S. Newport*), and Group D (includes *S. Typhi*, *S. Enteritidis* and *S. Dublin*). Serovars of *Salmonella* serogroups A, B, and D share a common mannose-rhamnose-galactose trisaccharide backbone. Distinct dideoxyhexose sugars linked to the mannose residues of the common side chain provide serogroup specificity. Thus, if the dideoxyhexose sugar linked to the mannose is a paratose, this results in immunodominant antigen "2", denoting a serogroup A *Salmonella* isolate. If the sugar linked to the mannose is an abequose, this results in an immunodominant antigen "4", denoting serogroup B *Salmonella*. Finally, if the sugar linked to the mannose is a tyvelose, this results in immunodominant antigen "9", denoting serogroup D *Salmonella*.¹²

Specific antibody responses against the O polysaccharide antigens of the conjugate, if protective, should provide some degree of protection against all the different serovar pathogens within that O serogroup. For example, both *S. Enteritidis* and *S. Dublin* serovars fall within O serogroup D. Immune responses against Group D O antigen should contribute to protection against both of these Group D serovars. CVD investigators have devised practical methods to purify COPS from attenuated "reagent strains" that have been engineered to enhance the yield of COPS and to facilitate the large-scale manufacture of these antigens under enhanced occupational safety.¹⁸ The vaccine candidates to be evaluated in this study are based on the COPS of *S. Typhimurium* (a Group B serovar) and *S. Enteritidis* (a Group D serovar).

The *S. Enteritidis* conjugate component in our trivalent vaccine is generated by 1-cyano-4-dimethylaminopyridinium tetrafluoroborate (CDAP) chemistry to link *S. Enteritidis* COPS to the FliC Phase 1 flagellin protein subunits of *S. Enteritidis* that had been derivatized with adipic acid dihydrazide (ADH) using carbodiimide. This strategy is similar to the approach used for MenAfriVac™, which is comprised of the group A meningococcus capsular polysaccharide linked to tetanus toxoid (TT).²⁰ MenAfriVac has been administered to infants, toddlers, children, and adults in countries within the African Meningitis belt.²¹ CDAP linkage and ADH derivitization are also used by GlaxoSmithKline (GSK) Vaccines in preparing their multivalent pneumococcal conjugate vaccine (Synflorix™) and by Sanofi Pasteur Vaccines in preparing their quadrivalent meningococcal conjugate vaccine (Menactra™). Synflorix™ and Menactra™ have extensive track records of safety in infants, children and adults, including in sub-Saharan Africa. Similarly, experimental *S. Paratyphi A* conjugates generated at the National Institute of Child Health and

Human Development by John B. Robbins and colleagues in the late 1990s consisted of *S. Paratyphi A* COPS linked to tetanus toxoid carrier protein and utilized ADH as a linker with CDAP conjugation.²² The *S. Paratyphi A* conjugates prepared by the Robbins Laboratory at NICHD were safe and immunogenic in Phase 1 and Phase 2 clinical trials that involved adults, teenagers and children 2-4 years of age.²³ Interestingly, among the pre-school age children who received either one or two spaced doses of *S. Paratyphi A* conjugate 6 weeks apart, there was no evidence of a booster effect following administration of the second dose of conjugate.²³

The *S. Typhimurium* conjugate component in our trivalent vaccine is generated by modification at the polysaccharide terminal 2-keto-3-deoxyoctonate (KDO) carbonyl with an amineoxyl linker. The amineoxyl forms an oxime bond with the KDO ketone that is further reduced with sodium cyanoborohydride. *S. Typhimurium* FliC protein (phase 1 flagellin subunit) is derivatized with the amine reactive reagent succinimidyl 4-maleimidylbutyrate (GMBS) to introduce a maleimide moiety that is then linked to the reactive sulfhydryl of the derivatized COPS molecule via formation of a thioether bond. There is no FDA-licensed conjugate vaccine for human use that utilizes the specific method of conjugation employed for our *S. Typhimurium* glycoconjugate. However, a synthetic Hib capsular polysaccharide-based glyconjugate vaccine that is licensed and manufactured in Cuba (and that is pre-qualified by the WHO) utilizes a maleimide linker.²⁴ We have extensive pre-clinical experience with *S. Typhimurium* conjugate vaccines prepared utilizing this approach, and have published reports that document the tolerability and immunogenicity of such conjugates in animal models.^{15,16,19,25} John Robbins and team at the NICHD also successfully used amineoxyl linker based approaches for synthesis and preclinical evaluation of COPS-based conjugates for a variety of gram-negative pathogens.^{26,27}

The *S. Typhi* conjugate component in our trivalent conjugate vaccine is essentially Typbar-TCV™, a Vi conjugate vaccine generated by carbodiimide-mediated modification of *S. Typhi* Vi polysaccharide with ADH that introduces reactive hydrazide groups that are then used to link to tetanus toxoid (TT) via a second carbodiimide step. Typbar-TCV is a licensed typhoid vaccine in India and a number of other countries and has been extensively used in pediatric and adult populations.²⁸ The World Health Organization conferred pre-qualification status for Typbar-TCV on January 3, 2018.^{14,29} It is now a vaccine which can be procured by United Nations agencies.

Therefore, CVD investigators have devised novel candidate core-O polysaccharide-flagellin protein conjugates as a vaccine strategy for preventing iNTS and we have combined the iNTS conjugates with a Vi-TT conjugate (Typbar-TCV) to create a Trivalent Conjugate vaccine for preventing invasive iNTS disease and typhoid fever.

[figure not shown]
